**Table 1: Schedule of Trial Procedures: Double-Blind Phase (Continued)**

Visit Type a	Screening (Day -30 to Day -1)	Day 0 b	Visit W2	Visit W6	Visit W12 c	Visit W14	Visit W18	Visit W24 d / LTSE D1/ EOT e	FU (4 wks) f
Visit Windowg	≤30d		±3d	±1wk	±1wk	±1wk	±1wk	±1wk	±1wk
Dispense Investigational Product		X q			X			X r	
Investigational Product Accountability/ Compliance s			X	X	X	X	X	X	
Laboratory Evaluationst									
Serum Chemistry, Hematology, & Coagulation Parameters	X u	X	X	X	X	X	X	X	X
FGF-19		X			X			X	
CRP		X			X			X	
ELF Markers & Other Analytes v		X			X			X	
Plasma Bile Acids		X			X			X	
C4		X			X			X	
PK w					X			X	
Apolipoprotein & NMR Lipoprotein Panel		X			X			X	
Dipstick Urinalysis	X	X			X			X	
Urine Pregnancy Test x	X	X			X			X	X
Fecal Sample y		X			X			X	
Genetics Study z		X						X	

- a Subjects must be fasted prior to all clinic visits (except Screening) and investigational product should not be administered prior to clinic visits (see [Section 8.1](#)).
- b Day 0 must occur by Day 31 for a subject to be eligible to continue in the trial.
- c Week 12 is the Dose Titration visit.
- d The Week 24 visit is the final visit during the DB treatment period. For subjects who continue into the LTSE, the Week 24 visit is also Day 1 of the LTSE, and unblinding occurs after the Week 24/LTSE Day 1 procedures have been completed (except dispensing of open-label investigational product).
- e End of treatment (EOT) visit is completed for any randomized subject who discontinues the study prior to reaching Week 24 of the DB phase; this should occur as close as possible to the final dose of investigational product. If a subject discontinues on the day of a scheduled trial visit, the procedures from the scheduled visit will be recorded as EOT in the CRF.
- f Follow-Up visit: If a subject discontinues the study prior to the end of Week 24 or does not proceed into the LTSE, he/she returns to the site for a Follow-Up visit, which should occur 4 weeks ( $\pm 1$  week) after her/his last dose of investigational product.
- g Timing of all visits is relative to Day 0.
- h Height is measured at the Screening visit only.
- i Vital signs: oral temperature, sitting heart rate (HR), respiratory rate, and sitting blood pressure ([BP] systolic and diastolic). When taking HR, respiratory rate, and BP readings, subjects should be seated quietly for a minimum of 3 minutes before the readings are taken.
- j TE: at trial sites where the Fibroscan® TE device is available. TE has a 5-day visit window. For the Day 0 assessment, TE should occur either on Day 0 or within 5 days prior to Day 0. For the Week 24 assessment, the TE should occur within  $\pm 5$  days of the onsite visit if it is not possible to schedule the TE on the same day as that visit, but the visit(s) should remain within the overall visit window.
- k Hepatic ultrasound has a  $\pm 5$ -day visit window (ie, if it is not possible to schedule the ultrasound on the same day as the onsite visit, it may occur within 5 days on either side of the visit, but the visit(s) should remain within the overall visit window).
- l Partial Mayo score completed only for subjects with UC.
- m Subjects with UC will be asked to complete a diary the day prior to their next trial visit, recording details since their last scheduled visit. Subjects with CD should complete the diary in the 7 days prior to their next clinic visit. Diary card data from the Screening period are collected at the Day 0 visit.
- n CDAI completed only for subjects with CD.
- o Questionnaire completed by the subject.
- p Adverse events will be collected from the time that signed informed consent is obtained.
- q All subjects are instructed to administer the first dose of investigational product on Day 1 and at approximately the same time of day for the duration of the trial (see [Section 8.1](#)).
- r Investigational product is dispensed only for subjects who continue into the LTSE. (Dispensing of open-label investigational product occurs after completion of the Week 24/LTSE Day 1 procedures and the subsequent unblinding of the subject's treatment allocation.)
- s Investigational product accountability/compliance will include review of tablets and bottles dispensed and returned at each clinic visit
- t All laboratory samples (except urine and serum pregnancy test, if applicable) are analyzed by the Central Laboratory.
- u IgG4 is included in the assessment panel at Screening only.
- v Other analytes includes an additional blood sample for exploratory analysis.
- w PK samples will be collected from those subjects who have consented for PK sampling procedures. Please refer to [Section 10.5](#) for a schedule of sampling.
- x For female subjects of child bearing potential, a urine  $\beta$ -hCG test is used. If the urine test is positive, it is to be repeated as a serum pregnancy test. See [Section 7.1](#) for procedures to be followed for a subject whose pregnancy is early terminated and wishes to continue in the trial.
- y Fecal sample: for measurement of calprotectin and gut fecal microbiome; provision of a fecal sample by subjects is not mandatory. The subject should be instructed to collect a fecal sample within 2 days of the scheduled visit, as described in the laboratory manual.
- z Genetics study: blood samples will be collected from those subjects who have consented for RNA sampling procedures.

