**For Subjects Participating in the LTSE:**

- Re-confirm their consent to participate in the LTSE phase of the trial.
- Unblind the subject's treatment allocation in IWRS (as detailed in a separate trial document) and document the dose of OCA on which the subject will commence the LTSE.
- Assess investigational product compliance and perform accountability; retrieve used bottles and document returns.
- Dispense indicated bottle(s) of investigational product.
- Subjects with UC or CD: provide the appropriate diary card and request this is completed for the 7 consecutive days prior to their next scheduled visit (for subjects with CD) and the day prior to their next scheduled visit (for UC subjects).
- Reiterate dosing instructions and advise the subject:
  - NOT to take investigational product on the morning of the next visit, and
  - To bring the investigational product bottle(s); and
  - To fast overnight (at least 8 hours) prior to the next visit. Fasting is required prior to all trial visits, but water is permitted, and the subject should dose at each visit after all assessments have been performed.

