#### **Pre-Titration Visit**

The Pre-Titration visit occurs approximately 1 week prior to the scheduled LTSE visit to assess serum chemistry (ie, ALP and bilirubin) and complete all other laboratory assessments.

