#### **11.1.2. Relationship to Investigational Product**

The Investigator will document her/his opinion of the relationship of the AE to treatment with the investigational product using the criteria outlined in [Table 7](#). An AE for which there is a ‘reasonable possibility’ that the investigational product caused the AE is otherwise referred to as suspected adverse reaction (SAR). ‘Reasonable possibility’ means there is evidence to suggest a causal relationship between the investigational product and the AE.

If the relationship between the AE/SAE and the investigational product is determined to be “possible”, “probable” or “definite” the event will be considered to be related to the investigational product for the purposes of expedited regulatory reporting.

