10.2. Adverse Events (AEs)

All AE summaries will be restricted to treatment-emergent adverse events (TEAEs), which are defined as any AEs that newly appear, increase in frequency, or worsen in severity following initiation of study medication. If it cannot be determined whether the AE is treatment emergent due to a partial onset date, then it will be counted as treatment emergent. Verbatim terms on eCRFs will be mapped to preferred terms and system organ classes using MedDRA (version 17.1).

Summaries that are displayed by system organ class and preferred terms will be ordered by descending order of incidence for all OCA treated patients of system organ class and by preferred terms within each system organ class. Summaries of the following types will be presented by treatment group:

- Overall summary of TEAEs
- Subject incidence of TEAEs and the total number of entries by MedDRA system organ class and preferred term.
- Subject incidence of drug-related TEAEs by MedDRA system organ class and preferred term. Related AEs are those with relationships reported as “Definite,” “Probable,” “Possible,” or with a missing relationship.
- Subject incidence of serious adverse events (SAEs) by MedDRA system organ class and preferred term.
- Subject incidence of TEAEs leading to investigational product withdrawal or study discontinuation by MedDRA system organ class and preferred term. This is a subset of the AEs where Action Taken with Study Medication is checked as “Drug Withdrawn” or Subject Discontinued from Study is checked.
- Subject incidence of TEAEs leading to investigational product withdrawal by MedDRA system organ class and preferred term. This is a subset of the AEs where Action Taken with Study Medication is checked as “Drug Withdrawn”.
- Subject incidence of TEAEs leading to study discontinuation by MedDRA system organ class and preferred term. This is a subset of the AEs where Subject Discontinued from Study is checked.
- Subject incidence of TEAEs by MedDRA system organ class, preferred term, and maximum severity will be presented. At each level of subject summarization, a subject is classified according to the maximum severity if the subject reported one or more events. AEs with missing severity will be considered severe for this summary.

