10.4. Clinical Laboratory Evaluations

Clinical laboratory evaluations during the DB phase are assessed at the central laboratory. A listing of available laboratory reference/normal ranges for each laboratory parameter will be provided including age, sex, values with units. All analyses of lipoprotein will include fasted samples only.

Quantitative hematology, coagulation, serum chemistry, apolipoprotein and nuclear magnetic resonance (NMR) lipoprotein panel laboratory parameters will be summarized by treatment group in SI units using arithmetic summary statistics as described in [Section 6.2.1](#) at Baseline and at each scheduled DB post-Baseline visit. Change from Baseline will also be summarized in the same manner. Re-tests or unscheduled visit results after first dose of investigational product in the DB phase will not be summarized but will be included in the data listings.

In addition, shift tables (ie, low-normal-high at Baseline versus low-normal-high at DB post-Baseline Visit in a 3-by-3 contingency table) from Baseline to worst value, last value, and at each scheduled DB post-Baseline visit will be provided for hematology, coagulation, and serum chemistry by treatment group.

Urinalysis results will not be summarized but will be provided in a data listing.

Listings of all laboratory values will flag values outside of the normal range as high (H) or low (L) and indicate whether or not a value is clinically significant (CS), based on investigator judgment.

For laboratory test results that are below the quantifiable limits:

Imputed laboratory result = (numeric portion of the result) \times 0.9.

For laboratory test results that are above the quantifiable limits:

Imputed laboratory result = (numeric portion of the result) \times 1.1.

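### LTSE entrants are unblinded at the Week 24 visit with no requirement to judge the Week 24 laboratory panel first, so AEs from that panel may be classified with the allocation known

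*Protocol*

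**What the plan says.** For a subject entering the LTSE, the Week 24 visit is also LTSE Day 1. Table 1, footnote d, says that "unblinding occurs after the Week 24/LTSE Day 1 procedures have been completed (except dispensing of open-label investigational product". Footnote r gives the order that follows: "Dispensing of open-label investigational product occurs after completion of the Week 24/LTSE Day 1 procedures and the subsequent unblinding". In the visit list (Protocol 8.6.10, subjects participating in the LTSE) the step reads "Unblind the subject's treatment allocation in IWRS (as detailed in a separate trial document", and dispensing comes after it.

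On the laboratory side, Table 1, footnote t, says: "All laboratory samples (except urine and serum pregnancy test, if applicable) are analyzed by the Central Laboratory". No turnaround time is given. The nearest indication is the LTSE titration rule in Protocol 8.6.13: "The Pre-Titration visit occurs approximately 1 week prior to the scheduled LTSE visit to assess serum chemistry (ie, ALP and bilirubin".

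On judgement, Protocol 11.1.1.1 allows an abnormal laboratory finding to be an AE, and 11.1.2 says: "The Investigator will document her/his opinion of the relationship of the AE to treatment with the investigational product". SAP 10.2 then tabulates, by treatment group, "Subject incidence of drug-related TEAEs by MedDRA system organ class and preferred term", together with TEAEs by maximum severity. SAP 10.4 has the laboratory listings "indicate whether or not a value is clinically significant (CS), based on investigator judgment".

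**The concern.** Protocol 8.4 blinds the subject, the investigator and site staff for the subject's time in the double-blind phase. The Week 24 sample belongs to that phase, but the judgement made on its results may not be blinded. Nothing in the visit procedures asks for the results to be received, assessed and entered before the allocation is released, and no blinded assessor is named.

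The AE status, severity and relationship of a finding from the last double-blind panel may then be decided with the arm known, whereas the same decisions at Weeks 2, 6, 12, 14 and 18 are made blind. Subjects who stop early or decline the LTSE are not unblinded by this step, so the conditions of assessment also differ by disposition.

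Safety is a primary objective, and relationship is the AE field most open to knowledge of the arm. At stake is whether the double-blind tables of drug-related and maximum-severity TEAEs rest wholly on blinded judgements.

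**Working it through.** The plan states no figure on this point, so the check is mainly one of sequence, followed by arithmetic to give scale.

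**Sequence for an LTSE entrant (Protocol 8.6.10 and Table 1)**

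1. AEs are assessed and recorded as a Week 24 procedure. Events elicited at the visit are therefore recorded blind.
2. Blood is drawn for the central laboratory.
3. Once the remaining procedures are complete, the allocation is released in IWRS.
4. Open-label product is dispensed.
5. Laboratory results arrive at a time the documents do not state. The separate draw about one week before an LTSE titration visit suggests that same-day results are not expected.

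No link is specified between steps 3 and 5. That is the gap.

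**What depends on the judgement**

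- *Affected:* AE status, relationship and severity of findings first identified from the Week 24 panel, and hence the TEAE, drug-related TEAE and maximum-severity tables in SAP 10.2. The follow-up TEAE table there covers only subjects not continuing to the LTSE, so it does not separate these events.
- *Not affected:* the ALP endpoint, laboratory summaries and shift tables, which use central-laboratory values and reference ranges. The clinical-significance flag appears only in listings.
- *Tested AE analyses:* the log-rank comparisons for pruritus and dyslipidaemia (SAP 10.3) do not use relationship. A lipid finding first reported as an AE after unblinding could still count as a late dyslipidaemia event.

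**Share of panels**

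- Chemistry, hematology and coagulation are taken at Weeks 2, 6, 12, 14, 18 and 24: 1/6 = 17%.
- Apolipoprotein/NMR panels on treatment are at Weeks 12 and 24: 1/2 = 50%.
- With the plan's 20% dropout, 75 × 0.80 = 60 completers and 15 dropouts. Assume every completer enters the LTSE and each dropout contributes k on-treatment panels. The share is then 60 / (6 × 60 + 15k): 60/375 = 16.0% for k = 1, 60/405 = 14.8% for k = 3, and 60/435 = 13.8% for k = 5.

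**Scale of a possible shift**

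- One subject in a group of 25 is 1/25 = 4 percentage points.
- Let p be the proportion of a group whose only potentially drug-related TEAE comes from the Week 24 panel. Let d be the difference between arms in the chance of a related call that is due to knowing the allocation. The spurious difference is p × d. Neither value is in the documents. For assumed p of 2% to 20% and d of 10 to 50 points, the result runs from 0.02 × 10 = 0.2 points to 0.20 × 50 = 10 points.
- A panel-level illustration, also on assumed rates: 5% of panels show a reportable abnormality, and 30% of these are called related when blinded. Unblinded, the figures are 40% on OCA and 10% on placebo. The incidence of drug-related laboratory AEs over six panels is 1 − (1 − 0.015)^5 × (1 − 0.020) = 9.1% on OCA and 1 − (1 − 0.015)^5 × (1 − 0.005) = 7.7% on placebo, a gap of 1.4 points with identical laboratory data. Scaled by 80% for dropout, this is about 1.1 points, or 0.3 of a subject in 25.

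**The case against.** The strongest reply is that the exposure is narrow and the harm unproven. Most of this stands.

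- A reader might infer that results cannot be back before the code is released. The documents do not establish that. No turnaround is stated. The one-week interval is a scheduling rule for a different visit. Ultrasound and elastography may fall up to 5 days after the visit, which can delay completion of procedures. The unblinding steps are in a separate document not available here. What survives is that nothing requires the results to be judged first.
- A reader might take 17% or 50% of panels as the share of affected events. It is not. A TEAE must newly appear, become more frequent or worsen, so an abnormality already recorded and unchanged adds nothing at Week 24.
- A reader might infer that the SAP compares clinically significant laboratory values between arms. It plans no such comparison.
- The drug-related table is descriptive, with no test attached.
- A reader might infer that earlier AE records remain open to revision after unblinding. Protocol 12.6.1 places the database lock after all subjects finish the double-blind phase, and Table 3 expects about 18 months of enrolment, so there is time for this. But the documents do not state the data-entry edit rules, so it is a possibility only.

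The reply does not remove the gap. The judgements concerned feed by-arm tables for a primary objective, and the SAP has no means of identifying which of them were made unblinded.

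**Conclusion.** The point holds as a risk, not as demonstrated bias. For LTSE entrants, AE status, severity and relationship for findings from the Week 24 panel may be judged with the allocation known, because no step requires those results to be reviewed before unblinding. The exposure is 1 of 6 on-treatment chemistry panels.

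The existence, direction and size of any bias in the drug-related and maximum-severity tables cannot be established from the documents. The 0.2 to 10 point range and the 1.1 point illustration rest entirely on assumed rates of abnormality and of related calls. The firm figure is that one reclassified subject moves a group of 25 by 4 points. The stronger conclusion, that the drug-related AE comparison is biased against OCA, is not supported. The efficacy result and the laboratory value analyses are untouched. This is an inexpensive improvement to the SAP, best prespecified before the double-blind lock because afterwards it would be post hoc.

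**What to change.** In SAP 10.2, keep the full tables as planned and prespecify sensitivity versions of the TEAE, drug-related TEAE and maximum-severity tables, with these rules:

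1. Exclude AEs first entered after that subject's unblinding in IWRS, including those first identified from the Week 24 laboratory panel.
2. List the excluded events separately by arm. This also shows whether any are dyslipidaemia terms.
3. For AEs entered before unblinding and edited later, use the relationship and severity recorded at unblinding.
4. State that excluded AEs do not fall under the SAP 10.2 rules that count a missing relationship as related and a missing severity as severe.

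The main tables should not be rebuilt on pre-unblinding values. An AE first entered after unblinding has no such value, so the missing-data rules could turn it into a related, severe event, and genuine updates from the AE follow-up required by Protocol 11.1.8 would be lost. The clinical-significance listings need no change.

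The cost is SAP wording, a derived flag and a few extra tables. The flag needs the IWRS unblinding time and the AE entry and edit times; that these are held electronically is an assumption to confirm. The downside is that the sensitivity tables lose events first detected at Week 24, which remain visible in the full tables and the by-arm list. Visit procedures, dosing and sample size do not change.

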#### **8.6.10. Week 24/LTSE Day 1 Procedures**

- Assess and record AEs.
- Record current concomitant medications.
- Perform a physical examination, including weight.
- Record vital signs.
- Perform a standard 12-lead ECG.
- Perform TE at sites where the Fibroscan® TE device is available.
- Perform hepatic ultrasound to assess bile duct patency.
- For subjects with UC: obtain partial Mayo score (excluding endoscopy).
- For subjects with CD: complete CDAI assessments and assign CDAI score.
- Administer pruritus VAS subject questionnaire and 5-D Itch questionnaire.
- Subject to complete the Subject Research Questionnaire.
- Obtain blood samples for:
  - Serum chemistry, hematology, and coagulation
  - FGF-19
  - CRP
  - ELF markers and other analytes
  - Plasma bile acids and C4

- Apolipoprotein and NMR lipoprotein panel
- Genetics study (if subject has consented to provide a sample for RNA analysis)
- For sites participating in PK sampling: obtain samples for PK analysis (see [Section 10.5](#) for sampling schedule).
- Obtain urine sample for dipstick urinalysis.
- Perform a urine based  $\beta$ -hCG pregnancy test in females of childbearing potential. If the urine pregnancy test is positive it should be repeated as a serum pregnancy test.
- Obtain fecal sample for calprotectin and microbiome assessments (in subjects willing to provide a fecal sample).
- Verify that the subject has fasted for at least 8 hours.
  - Record fasting status in the source and CRF.
  - If the subject reports having eaten within 8 hours, document accordingly in the source and CRF and remind the subject that fasting is required prior to all trial visits, but water is permitted.
- Record the visit in the IWRS and indicate if the subject plans to participate in the LTSE.

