6. GENERAL ANALYSIS CONSIDERATIONS

6.1. Data Reporting

The statistical analyses will be reported using summary tables, figures, and data listings.

Laboratory units will be summarized and presented both in conventional units (CV) and in the international system of units (SI).

Individual subject data obtained from the electronic case report forms (eCRFs), external laboratory data, and any derived data (such as change from Baseline and percent change from Baseline) will be presented in data listings by subject. Data from all assessments, whether scheduled or unscheduled, will be listed by subject and visit. Unscheduled visits and visits occurring more than one day outside protocol defined window will not be included in the table summaries, excluding transient elastography measurements.

The analyses described in this plan are considered a priori, in that they have been defined prior to database lock of the DB phase. Post hoc analyses will be labeled as such on the outputs and identified in the CSR.

All analyses and tabulations will be performed using SAS® Version 9.2 or higher. PK parameters will be estimated using Phoenix® WinNonlin® Version 6.3. The following processes will be employed to validate statistical outputs: derived datasets (both tabulation datasets and analysis datasets), summary tables, and data listings will be verified through independent programming; graphical displays will be compared against supporting summary tables; and all outputs will undergo a senior-level statistical review. The process includes confirmation that statistically valid methods have been implemented and that all data manipulations and calculations are appropriate and accurate. Checks will be made to ensure accuracy, adherence to this SAP, consistency within tables, and agreement between tables and their corresponding data listings. Upon completion of validation/verification and quality review procedures, all documentation will be collected and filed in the study master file by the project statistician or designee.

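### The ±5-day window for the Week 24 elastography is not reconciled with the unblinding tied to that visit, and the SAP has no rule for scans taken after the blind is broken

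*Protocol*

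**What the plan says.** - **Day 0 scan.** Table 1, footnote j: "For the Day 0 assessment, TE should occur either on Day 0 or within 5 days prior to Day 0". It can move only earlier.
- **Week 24 scan.** The same footnote allows ±5 "days of the onsite visit if it is not possible to schedule the TE on the same day as that visit", with the limit "but the visit(s) should remain within the overall visit window". Table 2, footnote i, repeats the ±5-day allowance for the LTSE schedule, which includes LTSE Day 1.
- **Visit checklist.** Section 8.6.10 covers Week 24 and LTSE Day 1 together. Its procedures include "Perform TE at sites where the Fibroscan" device is available. For LTSE entrants it continues with unblinding in the IWRS and then "Dispense indicated bottle(s) of investigational product". Section 6.4.2 ties the breaking of the blind to completion of the Week 24 visit.
- **Stated order.** Table 1, footnote d: "unblinding occurs after the Week 24/LTSE Day 1 procedures have been completed (except dispensing of open-label investigational product"). Footnote r: "Dispensing of open-label investigational product occurs after completion of the Week 24/LTSE Day 1 procedures and the subsequent unblinding". Table 2, footnotes c and o, say the same.
- **Analysis.** SAP 6.1: "visits occurring more than one day outside protocol defined window will not be included in the table summaries, excluding transient elastography measurements". SAP 9.2.3 uses TE in an ANCOVA and, at Week 24, in a Cochran-Mantel-Haenszel (CMH) comparison of OCA with placebo. There, any change from Baseline below zero counts as improvement.

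**The concern.** At Day 0 the scan is protected by only being allowed to move earlier. At Week 24 it may move later, past the visit at which the checklist breaks the blind and hands out open-label OCA. Table 4 has placebo and 3 mg subjects starting the LTSE at 5 mg.

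TE is performed by trained site staff (Protocol 10.3), and no blinded operator is required. Section 8.4 keeps site staff blinded only during the subject's double-blind participation. A scan taken after the visit could therefore be done by someone who knows the arm, and possibly after some open-label doses, yet be analysed as a double-blind Week 24 value. Because the improvement cut is at zero, a small shift can move a subject across it. TE is also done only at equipped sites, so a few affected subjects could weigh more than in a whole-trial endpoint.

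**Working it through.** The plan gives no figure that depends on this point, so there is none to reproduce. The check is date arithmetic and a comparison of passages.

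**1. How late can the scan be?** Week 24 is Day 168 from Day 0. With ±7 days the visit window is Day 161 to Day 175. The latest permitted scan is the earlier of visit day + 5 and Day 175.

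| Onsite visit | Days allowed after the visit |
|---|---|
| Day 161 to 170 | 5 |
| Day 171 | 4 |
| Day 172 | 3 |
| Day 173 | 2 |
| Day 174 | 1 |
| Day 175 | 0 |

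A scan after the visit is thus allowed for every visit day except the last.

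**2. Do the passages fit together?** TE is a Week 24 procedure. Under footnotes d and r, a pending scan means the procedures are incomplete, so unblinding and dispensing should wait. Footnote j does not say so. Section 8.6.10 runs all three steps in one visit, with no instruction to hold the last two and no second attendance for them. LTSE visits are timed from LTSE Day 1, which is the Week 24 visit (Section 8.6.1). A site can follow footnote j and the checklist and still break the order in footnotes d and r.

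**3. Could a site wait?** Week 12 supply is 4 bottles × 100 tablets = 400 tablets (Sections 9.2 and 9.4.1). At 4 tablets a day (Section 8.1) that is 400 / 4 = 100 days. The nominal need is 84 + 5 = 89 days. The most the windows allow is Day 77 to Day 175, or 98 days. Supply does not prevent waiting.

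**4. Exposure if the site does not wait.** Take a scan k days after the visit, before that day's dose. It follows k doses if dosing starts on the visit day, or k − 1 if it starts the next day. For k = 5 that is 5 or 4 doses; for k = 1 it is 1 or 0.

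**5. What the SAP does with it.** A scan inside both limits in step 1 is in window and is kept without needing the exemption. A scan beyond the window is kept because of it. Neither is checked against the date of unblinding or of the first open-label dose.

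**6. Size.** The documents give neither the share of late scans nor any effect of a few days of OCA on stiffness. If a share f of placebo scans were shifted by e stiffness units, the placebo mean would shift by f × e. Over an assumed range this runs from 0.05 × 0.1 = 0.005 to 0.5 × 1.0 = 0.5 units. That shows the form of the dependence and is not an estimate. The only onset figure given is for ALP in primary biliary cirrhosis, from 2 to 4 weeks (Protocol 4.6.2, duration of dosing).

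**The case against.** The best defence is that the order is already fixed. Footnotes d and r, with their Table 2 counterparts, put unblinding and dispensing after the Week 24 procedures, and TE is one of them. No passage requires same-day unblinding while a scan is pending, footnote j allows for more than one attendance, and supply lasts long enough. This stands in part: a scan after unblinding would breach the stated order.

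A reader might therefore infer too much, in three ways.

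- **That the protocol permits placebo Week 24 scans to be unblinded and on OCA.** It does not clearly permit this. It leaves a gap through which it could happen.
- **That there is no upper limit on the scan date.** The protocol caps it at 5 days and the ±1 week window. SAP 6.1 only governs inclusion in tables, and SAP 8.2 still records out-of-window assessments as deviations.
- **That every late placebo scan is on active drug.** The 5 mg start is the intention, departures can be discussed with the Medical Monitor, and a next-day scan might precede the first dose.

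The bias mechanism is also only partly supported. Nothing shows stiffness responding within 5 days, and if it fell in placebo subjects the contrast with OCA would shrink. The documents do not say that the operator is told the allocation. TE is secondary and outside the testing hierarchy, and same-day scanning is the default.

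The defence does not answer two points: a site is never told that a deferred scan holds the blind, and the SAP has no rule for a scan taken after it is broken.

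**Conclusion.** The passages conflict in practice and need to be reconciled. A post-visit scan is allowed by up to 5 days, the checklist breaks the blind at the visit, and the SAP would keep the resulting value in the double-blind Week 24 ANCOVA and CMH test with no flag tied to unblinding.

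The size cannot be stated, and the direction of any operator effect is uncertain. The conclusion assumes that at least some sites would unblind on the visit day with a scan outstanding. Possible operator knowledge of the arm is the firmer concern; a drug effect within 5 days is unproven. The reach is limited to LTSE entrants at Fibroscan sites whose scan is late, on a secondary endpoint. The primary ALP analysis is untouched. This is a cheap improvement and not a threat to the trial's main conclusion.

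**What to change.** **Protocol.** In Table 1, footnote j, and in Table 2, footnote i, for LTSE Day 1, have the Week 24 TE done on the visit day or within the 5 days before it, and before unblinding. This matches the Day 0 rule and brings the footnote into line with footnotes d and r.

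**SAP.** In 6.1, limit the TE exemption to scans dated before unblinding and before the first open-label dose. Apply the same date check to scans inside the visit window, since those are kept without the exemption. List later scans and leave them out of the Week 24 ANCOVA and CMH test, or show them only in a sensitivity analysis. The SAP change protects the analysis even if visits are already under way.

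**Cost.** Two footnotes and a short SAP rule. Sites must book the scan on or before the visit, and a few late scans are lost from the main Week 24 analysis.
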